### 17.3 Statistical Analysis:

We will first empirically verify that randomization was successful by testing whether trends in the outcome are equal across the study arms in the 12 months prior to the start of the intervention period. Second, we will present descriptive statistics by intervention arm of the outcomes, basic characteristics of the PCPs, and clinical and demographic characteristics of the patients seeking care whose visits meet the inclusion criteria. We will also produce graphs of the unadjusted trends in the outcomes by month over the study period, and broken down by study arm.

We will run separate analyses for the opioid-naïve population and the current opioid user population. The analysis sample for the opioid-naïve population will be primary care visits for patients who have not had an active opioid prescription in the six months prior to the visit, and no cancer diagnosis in the 12 months prior to the visit. In order to identify the visits that plausibly might lead to an opioid prescription, we will restrict to primary care visits that have a recorded diagnosis that occurs regularly in opioid-prescribing visits. We are defining those diagnoses as diagnoses that were associated with at least a 3% opioid prescribing rate among opioid-naïve primary care visits across all FMG and UMP primary care clinics over a 12 month period and there were at least 25 opioid orders in visits with the diagnosis for all visits in the study clinics during the 12-month period before the study, excluding diagnoses for current opioid use, which is intended to have very high sensitivity for capturing chronic pain-related diagnoses, but low specificity. We have already created this list, which includes 294 specific diagnoses with pain-related diagnoses the most common.

The analysis sample for the current opioid user sample will be all primary care visits for patients with an active opioid prescription, excluding patients with a cancer diagnosis in the 12 months prior to the visit. We will include both in-person visits along with virtual (telephone or video) visits for all analyses.

#### *Primary Outcome Analysis*

To test our primary hypotheses, we will fit mixed effects logistic regression models using data from the 12-month pre-intervention period, and the post-intervention period prior to any second-stage randomization (the model for the current “high risk” opioid group will be multinomial logistic regression due to the 3-category outcome). All models will include fixed effects for whether the encounter was at an intervention arm clinic, an indicator for whether the measurement was after the interventions began, and their interaction. The interaction is the primary measure of the intervention effect. These models include random effects for clinic and PCP (nested in clinic) to account for within-clinic and within-provider correlation. Because of the cluster-randomized design with a moderate number of clinics, residual imbalances in patient and PCP-characteristics among the randomized groups may exist. The primary analysis model will adjust for characteristics at all levels of the hierarchy including clinic-level (indicators for the four systems), PCP-level (clinician type [MD/DO, NP, or PA], sex, and length of tenure in medicine), and patient-level (age, sex, race/ethnicity, insurance status, and in-person or virtual visit). Separate models will be fit to assess the PDMP integration and choice architecture intervention and for the opioid-naïve and current, high-risk opioid users. In each model, the intervention group pools across two arms of the factorial design (e.g., the choice architecture intervention pools across arms 2 and 4) and the control condition pools across the remaining two groups (e.g., arms 1 and 3 to continue the example). A Bonferroni correction will adjust inference for multiple comparison across two different populations (opioid naïve and current, high-risk opioid users) but we will not adjust for multiple tests across the two different interventions.

As an exploratory analysis, we will assess whether PCP characteristics (clinician type and tenure in medicine) and patient characteristics (age, sex, and race/ethnicity) moderate the interventions’ effect. Tests for treatment effect heterogeneity will be implemented by adding the interaction between the potential moderator and the intervention indicator to the models for the primary

outcome (adjusting for the same factors described above). The effect of the intervention within subgroups formed from the potential moderators will be estimated by fitting separate models within each subgroup.

Subgroup analyses will not be adjusted for multiple comparisons; they are supportive to the primary outcome analysis. Subgroup analyses will be interpreted with caution due to limited power and uncontrolled type I error.

If the study proceeds to the second stage of randomization, we will fit mixed effects logistic regression models using data from 12 months pre- and post-intervention. All models will include fixed effects for intervention arm (control, continued intervention, 50% intervention, or intervention turned-off), indicators for whether the measurement was after the initial interventions began or after the second stage randomization, and their interaction. The interaction is the primary measure of the intervention effect. The models will include the same random effects and covariate adjustment as above.

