#### *Interim Outcome Analysis Plan*

The DMC is responsible for assessment of the efficacy of the interventions during the course of the study i.e. interim analyses of efficacy endpoints. The study protocol version 1.2 pre-specifies the following interim analyses: The DMC will be asked to recommend graduation to the second stage of randomization when there is clear and substantial evidence of a treatment difference. As a guideline, the Lan-DeMets spending function analog of the Pocock boundaries will be used to monitor the primary endpoint comparison for the primary aims. The statistical analysis plan is given in the protocol. In brief, we will fit mixed effects logistic regression models of the primary outcome (described below) for opioid-naïve patients using data from the 12 months of the pre-intervention period, and through December 31, 2020 (approximately 4 months of post-intervention data). These models will include fixed effects for whether or not the encounter was at a clinic in the intervention a given intervention arm or received both interventions, indicators for study month to account for secular trends, and an indicator for whether an observation takes place in an intervention arm clinic and in the post-intervention period. These models will include random effects for clinic and PCP (nested in clinic) to account for within-clinic and within-PCP correlation.

We propose a single interim analysis occurring sometime shortly after January 1, 2021, using data through December 31, 2020. The planned boundaries are given below. The advantage of using the Lan-DeMets spending function is that this permits the DMC during the course of the study to require more frequent interim analysis and preserve type I error. If more interim analyses are desired by the DMC, the Lan-DeMets spending function will be recalculated and provided with each DMC report.

Interim Analysis	Critical Z-score	Nominal One-sided p-vale	Alpha Spent
1	2.16	0.0155	0.0155
Final	2.20	0.0139	0.0095

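### The final opioid-naïve model drops the interim model's study-month adjustment without explanation, losing a nearly free protection against a small bias if visit timing differs between groups

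*Combined protocol and SAP*

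**What the plan says.** Section 17.1, Interim Outcome Analysis Plan, describes a mixed logistic model for the opioid-naïve primary outcome, fitted to 12 months before the intervention and about 4 months after. Time enters as "indicators for study month to account for secular trends". The effect term is "an indicator for whether an observation takes place in an intervention arm clinic and in the post-intervention period". There are random effects for clinic and for PCP within clinic. The model is introduced as a short account of the protocol's own plan: "The statistical analysis plan is given in the protocol. In brief, we will fit mixed effects logistic regression models of the primary outcome".

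Section 17.3, Primary Outcome Analysis, gives the final model. It has an arm term, "an indicator for whether the measurement was after the interventions began, and their interaction", and the same random effects. It then states: "The interaction is the primary measure of the intervention effect". A list of clinic, PCP and patient covariates follows, including visit mode (in-person or virtual). No month or other calendar term appears. The same terms serve the multinomial model for high-risk current users.

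Section 17.3 also plans a test of equal pre-period trends across arms and unadjusted monthly graphs by arm. Neither puts month into the effect estimate. Revision 5 in the revision history records minor analysis-plan changes made before data analysis began, but does not say whether the time term was among them.

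**The concern.** Both descriptions are current text, and one presents itself as a summary of the other, yet they handle time differently. At the interim each month has its own level. In the final model all pre months share one level and all post months share another, although the final window is longer: at least 18 months against about 16 at the interim.

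In the single-step model, a month in which prescribing is unusual for everyone cancels out of the arm-by-post contrast only if that month holds the same share of each group's visits. If one group had relatively more of its pre-period visits in such a month, part of the calendar effect appears as an intervention effect. Month indicators remove this whatever the visit volumes are. At stake is a small, avoidable bias in the primary estimate, and a primary model that differs from the one used at the interim look with no reason given.

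**Working it through.** **Inputs from the documents.** Exhibit 8 gives a 7% rate without intervention, 15% as the smallest relative reduction, and 15 eligible visits per provider per month as the lower volume. Section 17.2 gives 48 clinics in four equal arms and 10 providers per clinic. Pooling two factorial arms gives 24 clinics per group, so 24 × 10 × 15 = 3,600 visits per group per month.

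**Inputs assumed.** The documents give no visit counts by arm and month and no size for month effects. I take three of the 12 pre months as shifted by ln(1.3) = 0.26 log-odds in both groups, one group having 10% or 30% more visits in those months, and otherwise equal volume. The true effect is null, with 6 or 12 post months.

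**1. The plan's boundaries, reproduced first.** With one-sided alpha 0.025 and spending 0.025 × ln(1 + (e − 1)t), taking t = 0.5 gives 0.025 × ln(1.859) = 0.0155, so Z = 2.157. Solving for the final look with correlation √0.5 gives Z = 2.201, nominal p = 0.0139 and increment 0.0095. The table has 2.16, 0.0155, 2.20, 0.0139 and 0.0095. The information fraction of 0.5 is inferred from this match; the plan does not state it.

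**2. Effect scale.** A 15% reduction from 7% is 5.95%. In log-odds: ln(0.0595/0.9405) − ln(0.07/0.93) = −0.174.

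**3. Bias of the single-step model.** To first order, bias = (difference between groups in the share of pre visits falling in the shifted months) × (shift). Expected logistic fits on arm-by-month cells give the last three columns. Results are the same for 6 and 12 post months; signs are omitted because they depend on which group has the extra visits.

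| Extra visits in the three months | Share of pre visits | First-order bias | Fitted bias, single step | Fitted bias, month model | Single-step bias as % of 0.174 |
|---|---|---|---|---|---|
| 0% | 25.0% v 25% | 0 | 0 | 0 | 0 |
| 10% | 3.3/12.3 = 26.8% v 25% | 0.018 × 0.262 = 0.005 | 0.005 | 0 | 3% |
| 30% | 3.9/12.9 = 30.2% v 25% | 0.052 × 0.262 = 0.014 | 0.014 | 0 | 8% |

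**4. Range under other assumptions.** A larger shift of 0.5 log-odds with 30% more visits gives 0.028, or 16%. A different set, with trend, season, lower volume in the shifted months, shifts of 0.2 to 0.5 and 10% to 30% imbalance, gives 0.001 to 0.010, at most about 6%.

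**5. Cost in precision.** In the fits above with up to 30% imbalance, the standard error of the interaction rises by a factor of at most 1.002 when month indicators replace the single step.

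**6. Effect on the interim and final tests.** In simulation of 48 clinics, the two models' estimates on the same data correlate at 0.997 or higher. Multiplying the between-look correlation by k and using the boundaries from step 1, overall one-sided error is 0.0250 at k = 1, 0.0250 at 0.997, 0.0251 at 0.99 and 0.0259 at 0.90. Whatever the correlation, it cannot exceed 0.0155 + 0.0139 = 0.0294.

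**The case against.** The strongest reply is that this is a modelling preference. Concurrent randomized controls and the post indicator already remove any common pre-to-post change. With about 24 clinics per pooled group there is no particular reason to expect visit timing to differ. Visit mode and patient mix are adjusted for and could absorb part of a within-period shift, and the pre-trend test and monthly graphs would show a gross problem. All of this stands, and it is why the point is minor. It does not explain why an adjustment present at the interim is absent from the final model, and none of it replaces month in the effect estimate.

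Three stronger readings are tempting, and the documents do not support them.

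- A reader might infer that the final model ignores secular trend. It does not, for the reason just given.
- A reader might infer that changing the model between looks invalidates the Lan-DeMets boundaries or makes the two estimates non-comparable. Both models target the same arm-by-post contrast, and step 6 shows type I error essentially unchanged. Section 17.1 also offers the boundaries only as a guideline, and the interim look covered only the opioid-naïve primary outcome.
- A reader might extend the point to the PDMP model, which also has a single step. Those data are monthly counts per PCP, so each PCP contributes one record per month whatever the visit volume. The visit-timing mechanism does not carry over.

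It is also fair that the precision cost was checked only for a binary logistic model. The high-risk model is multinomial, the documents give no category frequencies, and the cost there is unknown.

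**Conclusion.** The discrepancy is real and unexplained, and its consequence is small. The single-step model is unbiased for the arm-by-post effect when both groups' visits are spread alike over months. Under the main assumed imbalance its bias is 3% to 8% of the smallest effect in Exhibit 8; the other assumed settings span from under 1% to 16%. These figures rest on assumed month shifts and visit imbalances, which the documents neither supply nor rule out. Because the adjustment costs almost nothing in the opioid-naïve model and already stands in the interim specification, restoring it is a worthwhile improvement. It is not the repair of a serious flaw.

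**What to change.** In section 17.3, for the opioid-naïve mixed logistic model, replace the post main effect with study-month indicators and keep arm by post as the effect, as at the interim. With 18 to 24 months of data this means 17 to 23 indicators in place of one term, at about 0.2% in standard error.

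For the multinomial high-risk model, do the same if it converges. If it does not, report a sensitivity analysis with a coarser calendar term such as quarter. The downside is that month terms enter two equations, 34 to 46 coefficients in all, which may be too many if a taper category is sparse.

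If the single indicator is kept as primary, state why the month terms were removed and report the month-adjusted opioid-naïve model as a named sensitivity analysis. No new data are needed.

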### Futility Analysis

There will be no formal futility analyses presented to the DMC. Given that these interventions have small potential adverse effects, the DMC will NOT be asked to recommend early termination for futility.

17.2 Power Analysis: The proposed design has sufficient power to detect clinically meaningful changes in opioid prescription practices from the main effects of the two interventions and the control group (10). All power calculations assume a two-sided test at the 0.05 significance level. Power for the Primary Aim (comparison of intervention arms to the control during months 1-6) is shown in Exhibits 2a-b assuming a total of 48 clinical are randomized (equal allocation between Arms 1-4) with a conservative estimate of 10 providers per clinic (~12 providers per clinic in the FHS/UMP system). The range of the number of visits eligible and the percentage of visits with an opioid prescription in the control arm (for both the opioid-naïve and opioid-using populations) were based on preliminary data from the EHR from a subset of clinics that will be randomized. Meeker et al. (1) assumed an intra-clinic correlation of 0.05 but that encounters within the same provider were not further correlated. We assumed the correlation for visits within the same clinic (but with different providers) was 0.025 and the within-provider correlation would be 0.075 as well as considering a more conservative scenario (correlation given on the logistic scale (11)). We assumed a 5% and 17% prescription rate in the control arm for the opioid-naïve and opioid-using populations, respectively, based on preliminary analysis of opioid prescribing in Fairview primary care clinics, and based on published research (12). We considered a difference in the percentage of eligible encounters with an opioid prescription between the intervention and control groups of 3.5% and 5% to be of clinical interest in the two populations. Exhibits 8 and 9 demonstrate that we have sufficient power across a wide range plausible scenarios and maintain adequate power even under smaller effect sizes. These calculations are also conservative as they assume 48 clinics, whereas we expect to enroll over 50 clinics.

We also have sufficient power to detect differences between 2.5 to 4 percentage points across the two intervention sets during the first 6 months of the intervention.

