#### *Secondary Outcomes Analysis: PDMP and Web Survey data*

For other EHR-derived secondary outcomes, we will use the same general modeling framework as for the primary outcome but will fit mixed effects logistic or linear models depending on whether the outcome was categorical or continuous.

To assess intervention effects on the frequency of checking the PDMP we will fit mixed effects Poisson regression models using data from the 12 months pre- and post-intervention. All models will include fixed effects for whether the PCP was at an intervention arm clinic, indicator for whether the month was during the intervention period, and their interaction. The models will adjust for clinician type, length of tenure in medicine, and health system indicators, and include random effects for clinic and PCP (nested in clinic) to account for within-clinic and within-provider correlation. As an exploratory analysis, we will assess whether PCP characteristics (clinician type and length of tenure) moderate the effect of the interventions using a similar process as the primary outcome.

A similar approach will be used for the web survey data, except we will fit mixed effect linear regression models using data from the pre- and post-intervention surveys. All models will include fixed effects for whether the PCP was at an intervention arm clinic, an indicator for whether the survey was the 12-month follow-up, and their interaction.

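### The interaction models name random effects for clinic and PCP only, so the standard error assumes that clinics within a pooled group change alike

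*Combined protocol and SAP*

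**What the plan says.** Section 5.1 randomises clinics. Section 17.3 (Primary Outcome Analysis) fits mixed logistic models, multinomial for high-risk opioid users, to 12 pre-intervention months and the post-intervention period. Fixed effects are group, period and their product, and "The interaction is the primary measure of the intervention effect". On clustering it says "These models include random effects for clinic and PCP (nested in clinic) to account for within-clinic and within-provider correlation". On the comparison, "In each model, the intervention group pools across two arms of the factorial design", with the other two arms as control. On multiplicity, "A Bonferroni correction will adjust inference for multiple comparison across two different populations".

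For other EHR secondary outcomes, "we will use the same general modeling framework as for the primary outcome". The PDMP Poisson models also "include random effects for clinic and PCP (nested in clinic) to account for within-clinic and within-provider correlation".

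Section 17.2 describes power for the "comparison of intervention arms to the control during months 1-6". It states: "We assumed the correlation for visits within the same clinic (but with different providers) was 0.025 and the within-provider correlation would be 0.075". It gives no correlation between a clinic's level before and after the start.

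No section names a clinic-by-period or PCP-by-period effect, a random slope, a cluster-robust variance, or a clinic-level or permutation test.

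**The concern.** A clinic intercept describes how far a clinic sits above or below average throughout. It drops out when the clinic's post level is compared with its own pre level. A PCP intercept drops out in the same way for PCPs seen in both periods; with turnover the cancellation is not complete. What remains in the interaction's standard error is mainly visit-level sampling error.

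If clinics in the same group move by different amounts for unmeasured reasons (staffing, local policy, unrecorded case mix), that variation belongs in the standard error of a clinic-randomised comparison. The stated model has no term for it. Confidence intervals would then be too narrow and the Bonferroni level would be exceeded, for the coefficient on which the trial's conclusions rest.

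**Working it through.** **Inputs.** From Section 17.2: 48 clinics in four equal arms, so 24 v 24 after pooling; 10 PCPs per clinic; correlations 0.025 and 0.075 on the logistic scale; 5% opioid-naïve prescribing. From Exhibit 8: 7% prescribing; 15 or 30 visits per PCP per month. From Section 17.3: 12 pre-months. Six post-months are taken from the months 1-6 window. The 2.5% level is 0.05/2. Assumed, because not in the documents: r, and an illustrative 3% endpoint rate.

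**Variances.** Residual π²/3 = 3.290; total 3.290/(1 − 0.075) = 3.557. Clinic: 0.025 × 3.557 = 0.0889. PCP: 0.05 × 3.557 = 0.1778.

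**The plan's own figures.**
- Exhibit 9 reproduces within 1 point as a post-only comparison of 10 v 30 clinics over 6 months with full clinic variance: 81.5/89.7/95.0% and 77.5/86.5/92.8%, against 81/89/95% and 77/86/93%.
- Exhibit 8 reproduces as 12 v 12 clinics, 12 months pre and 6 post, with no clinic variance in the contrast: 96.4/99.9/100/100% and 75.8/95.4/99.7/100%, against 96/100/100/100% and 76/95/100/100%.
- With 10% of the clinic variance in that contrast, the 96% cell falls to 82%. Post-only with full clinic variance, it is 24% (12 v 12) or 42% (24 v 24).
- A post-only calculation over 4 months with no clustering at all gives the same Exhibit 8 figures, because 1/12 + 1/6 = 1/4.

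The settings behind both reproductions are inferred; the plan does not state them.

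**Standard error of the interaction.** Let p be the outcome rate and v the visits per PCP per month.
- Sampling part, which is all that the intercept-only model sees: V_s = (2/24) × (1/12 + 1/6) / [10 v p(1 − p)].
- Part from unequal clinic changes: V_c = (2/24) × 2(1 − r) × 0.0889.
- Type I error: 2 × [1 − Φ(z/k)], with k = √[(V_s + V_c)/V_s] and z = 2.241 at the 2.5% level.

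Example with p = 0.07, v = 30, r = 0.95: V_s = 0.00107 (SE 0.033); V_c = 0.00074; true SE 0.043; k = 1.30; error 8.5%.

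| Rate, visits | r=0.99 | r=0.95 | r=0.9 |
|---|---|---|---|
| 7%, 30 | 3.6% | 8.5% | 14.7% |
| 7%, 15 | 3.0% | 5.3% | 8.5% |
| 5%, 30 | 3.3% | 6.8% | 11.4% |
| 5%, 15 | 2.9% | 4.5% | 6.8% |
| 3%, 30 | 3.0% | 5.0% | 7.8% |
| 3%, 15 | 2.7% | 3.7% | 5.0% |

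The SD of clinics' log-odds changes, √[2(1 − r) × 0.0889], is 0.042, 0.094 and 0.133 at these values of r.

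**Check by simulation** (7%, 30 visits, 200 trials per setting, intercept-only model with variances held at the assumed values). The model SE stayed at 0.031, while the actual SD of the estimate was 0.031, 0.042 and 0.053 at r = 1, 0.95 and 0.9.

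**Power once V_c is counted** (15% reduction, 15 visits, 24 v 24, 2.5% level, normal approximation, r = 1/0.95/0.9). At 7% the log-odds difference is 0.174 and V_s, with the lower post-period rate in the intervention group, is 0.00225, giving 92.2/82.5/72.7%. At 5% they are 0.170 and 0.00309, giving 79.5/69.6/61.0%. A t reference with 46 degrees of freedom lowers the 5% figures to about 77/67/58%.

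**The case against.** **The size is conditional, and the plan may be nearly right.** The documents contain neither a value of r nor evidence that clinics drift differently. At r = 0.99 the excess is small. This stands: the point is a missing safeguard, not a demonstrated error.

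**5-7% is not the endpoint's rate.** Section 3.1 counts only opioid prescriptions without a non-opioid alternative, a subset of prescribing. The prescribing rate is therefore an upper bound, and a rarer endpoint means less inflation. This also stands, and is why the 3% rows are shown.

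**Random effects could include slopes, and the plan adjusts for covariates and checks pre-trends.** No slope is named; if one is intended, a sentence settles it. Covariates absorb measured drift only. The pre-trend check compares arms and leaves the standard error unchanged.

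**Stronger readings that the documents do not support.**
- That Exhibit 8 proves a common change was assumed. Only three of its eight cells are below 100%, its settings are not stated, and a calculation with no clustering fits equally well.
- That pooling arms 2 and 4 shows the standard error is too small. An effect of PMP integration would make changes differ within each pooled group, but with equal allocation it is balanced between the groups, so it is not used here.
- That the correction costs no useful power. At the 5% rate with 15 visits, it does.

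**Conclusion.** The structural point holds with high confidence: as written, the interaction's standard error is valid only if clinics within a pooled group share a common change given the covariates, and nothing in the plan protects against a failure of that condition. The size is a sensitivity range. For the opioid-naïve outcome at the 2.5% level, the error runs from close to nominal at r = 0.99 to between 5.0% and 14.7% at r = 0.9, depending on endpoint rate and visit volume. The range assumes 24 v 24 equal clinics, 6 post-months, PCPs present in both periods and no covariates.

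No figure is given for high-risk opioid users, because the 17% is a prescribing rate and the frequencies of the three categories are not stated, nor for the PDMP counts. The interim model (Section 17.1) and the second-stage model share the structure but need no change: Section 5.5 shows that the interim review is done and the second randomisation dropped. The web-survey model is left out because its random effects are not spelled out. This should be fixed, but it does not show that the planned results would be wrong.

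**What to change.** In the primary, EHR secondary and PDMP models, add a clinic-by-period random effect, and a PCP-by-period effect where it can be estimated. Alternatively, base inference on a clinic-level change or permutation test, or on clinic-clustered robust standard errors with a small-sample correction. Report the estimated clinic-by-period variance in either case, so that readers can judge how much it mattered.

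Recheck Exhibit 8 for the pooled contrast, with a stated r and the 2.5% level. Exhibit 9 is consistent with full clinic variance and needs no change on this account.

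Cost: no new data. Intervals widen, some degrees of freedom are lost, and the multinomial model is harder to fit. In simulations of the opioid-naïve setting (16 scenarios of 2,000 null trials, r from 1 to 0.9), the added clinic-by-period term with 46 degrees of freedom kept the error at the 2.5% level between 1.2% and 3.0%. Power for a 15% reduction at 15 visits falls from about 92% at r = 1 to about 73% at r = 0.9 if the rate is 7%, from about 80% to about 61% if it is 5%, and is lower still if the endpoint is rarer.

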Exhibit 8. Power to detect a difference in proportion of eligible visits with an opioid prescription between intervention and control arms. Power calculations assume an opioid prescription rate in the no intervention arms of 7%.									
30 eligible visits/month/provider					15 eligible visits/month/provider				
	% reduction in opioid prescribing					% reduction in opioid prescribing			
Intra-clinic/ Intra-provider correlation	15%	20%	25%	30%	Intra-clinic/ Intra-provider correlation	15%	20%	25%	30%
0.025/0.075	96%	100%	100%	100%	0.025/0.075	76%	95%	100%	100%

Exhibit 9. Power to test a difference in proportion of eligible visits resulting in an opioid prescription between intervention and controls arms in opioid-using population (Primary Aim). Power calculations assume 40 clinics randomized equally to Arms 1-4 with 10 providers/clinic, the opioid prescription rate in the control arm was 17%.									
10 eligible visits/month/provider					5 eligible visits/month/provider				
	Difference in opioid prescription rate between control and intervention					Difference in opioid prescription rate between control and intervention			
Intra-clinic/ Intra-provider correlation	4.5%	5%	5.5%		Intra-clinic/ Intra-provider correlation	4.5%	5%	5.5%	
0.025/0.075	81%	89%	95%	0.025/0.075		77%	86%	93%	

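### The current-user primary model has no patient level, so the standard error of its arm-by-period interaction is not assured to be valid, and the error could run either way

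*Combined protocol and SAP*

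**What the plan says.** Section 17.3 makes the visit the unit of analysis. The current-user sample is "all primary care visits for patients with an active opioid prescription", less patients with a recent cancer diagnosis. The primary three-category outcome is then modelled for the high-risk subset by multinomial logistic regression. Data come from 12 months before the intervention and from the post-intervention period. The effect of interest is the interaction of intervention group and period.

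On correlation, the Primary Outcome Analysis says: "These models include random effects for clinic and PCP (nested in clinic) to account for within-clinic and within-provider correlation". Patient characteristics enter only as fixed covariates. Sections 17.1 to 17.3 contain no patient random effect, no patient-clustered or robust variance, and no rule limiting a patient to one visit.

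The power section (17.2) has the same two layers: "We assumed the correlation for visits within the same clinic (but with different providers) was 0.025 and the within-provider correlation would be 0.075".

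**The concern.** Patients with an active opioid prescription can return many times, so one patient may supply many rows. If a patient's visits resemble each other beyond what clinic, PCP and covariates explain, those rows carry less independent information than the model assumes. The standard error at risk belongs to the interaction, the plan's primary measure, in the population where repeat visits are likely to be most common. An error there affects the confidence interval and the test on which the current-user conclusion rests.

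The direction needs care. In a comparison of post-period rates alone, ignoring positive patient correlation makes intervals too narrow. In a before-after contrast, a stable patient effect partly or wholly cancels for patients seen in both periods.

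**Working it through.** **1. Does the plan's power figure already contain a patient layer?**

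Inputs from 17.2 and Exhibit 9:
- "All power calculations assume a two-sided test at the 0.05 significance level".
- "Power calculations assume 40 clinics randomized equally to Arms 1-4 with 10 providers/clinic, the opioid prescription rate in the control arm was 17" per cent.
- Correlations of 0.025 (same clinic) and 0.075 (same provider), described as "correlation given on the logistic scale".
- The contrast is "comparison of intervention arms to the control during months 1-6".
- "10 eligible visits/month/provider" in the left panel, 5 in the right panel.

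Total latent variance = (π²/3)/(1 − 0.075) = 3.557. Clinic variance = 0.025 × 3.557 = 0.0889. PCP variance = 0.05 × 3.557 = 0.1778.

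Variance per clinic = 0.0889 + 0.1778/10 + 1/(10·m·p(1−p)), with m = 6 × visits per month.

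For 17% against 12% at m = 60:
- Control: 0.0889 + 0.0178 + 0.0118 = 0.1185.
- Intervention: 0.0889 + 0.0178 + 0.0158 = 0.1225.
- With 10 control and 30 intervention clinics, SE = √(0.1185/10 + 0.1225/30) = 0.126.
- The log odds ratio is 0.407, so power = Φ(0.407/0.126 − 1.96) ≈ 89.7%.

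| Difference | 4.5 | 5 | 5.5 |
|---|---|---|---|
| Stated, 10 visits/month | 81% | 89% | 95% |
| Reproduced | 81.5% | 89.7% | 95.0% |
| Stated, 5 visits/month | 77% | 86% | 93% |
| Reproduced | 77.5% | 86.5% | 92.8% |

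The 10-against-30 layout is inferred (15 against 15 also fits). All six cells come out with clinic and PCP correlation alone, so the power calculation has no patient layer either. Adding one to this post-only comparison (assumed logistic-scale correlation 0.2 to 0.5, 1 to 6 visits per patient in six months) takes 89.7% to 82-89% and 86.5% to 72-86%.

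**2. The interaction, in closed form**

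Take a stable patient effect and equal periods. Let ρ be the within-patient correlation, k the visits per patient per period, and f the share of patients seen in both periods. Then

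true variance / model variance = (1 − ρ) + kρ(1 − f).

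This exceeds 1 only if f < 1 − 1/k, which is below 50% at k = 2, 67% at k = 3 and 83% at k = 6. With ρ = 0.2 (assumed) and k = 3:
- f = 1: 0.80, SE ratio 0.89.
- f = 0.5: 0.80 + 0.30 = 1.10, SE ratio 1.05.
- f = 0: 0.80 + 0.60 = 1.40, SE ratio 1.18.

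If the correlation decays, cancellation weakens. With monthly visits, correlation 0.3 falling 10% per month and full overlap, the SE ratio is 1.23.

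**3. Simulation per PCP**

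Assumed: 30 patients, 120 pre and 60 post visits (10 a month for 12 and 6 months), 17% rate, patient logit SD 0.7 to 1.5. The ratio is the true SD of the pre-to-post change over the visit-independent SE.

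| Setting | SE ratio |
|---|---|
| No turnover, equal visit counts | 0.88-0.97 |
| No turnover, unequal counts, each patient's frequency stable | 0.99-1.01 |
| No turnover, visit frequency redrawn after the intervention begins | 1.07-1.27 |
| No turnover, between-period patient correlation 0.7 | 1.05-1.21 |
| 30-60% turnover, unequal counts | 1.05-1.34 |

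**4. Simulation of 40 clinics × 10 PCPs, 12 months pre and 6 post, no true effect**

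A linear stand-in for the planned model, with PCP intercepts and no patient effect. SE ratio by patient overlap between periods:

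| Latent correlation, visit interval | 0% | 50% | 75% | 100% |
|---|---|---|---|---|
| 0.2, monthly | 1.29 | 1.18 | 1.10 | 0.97 |
| 0.2, every 3 months | 1.11 | 1.05 | 0.97 | 0.93 |
| 0.4, monthly | 1.69 | 1.36 | 1.13 | 0.90 |
| 0.4, every 3 months | 1.20 | 1.02 | 0.96 | 0.89 |

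**5. Effect on the test level**

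The Bonferroni correction over two populations gives 0.05/2 = 0.025 each, critical value 2.241. The actual level is 2[1 − Φ(2.241/ratio)]:
- ratio 1.05: 2[1 − Φ(2.135)] = 3.3%
- ratio 1.31: 2[1 − Φ(1.711)] = 8.7%
- ratio 0.90: 2[1 − Φ(2.490)] = 1.3%

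**The case against.** The strongest reply is that the estimand is a before-after interaction and that long-term users are the patients most likely to be seen in both periods. A stable patient effect then cancels, and the planned interval is correct or conservative. This stands as far as it goes: ratios of 0.88 to 1.01 appear above when there is no turnover and visiting is stable. A reader might infer from the missing patient term that the intervals are simply too narrow. The documents do not support that, because they give no visits per patient, no overlap and no within-patient correlation.

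Further limits also stand:
- The outcome is an event at a visit (a reduction in dose, and of what kind). One taper could make another more or less likely at the next visit, so the size and even the sign of the within-patient correlation are assumed.
- Exhibit 9's visit rates are for opioid users generally. The primary model covers the narrower high-risk group, whose visit volume is not given.
- The simulations use a binary or linear stand-in, not the multinomial mixed model.
- Error rates worked out at 5% would ignore the Bonferroni level that 17.3 applies.

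What the reply does not show is that cancellation can be relied on. Eligibility is judged visit by visit (active prescription, cancer history, dose or benzodiazepine co-use), so patients can enter and leave. A taper changes the prescription against which the next visit is judged. The periods may also differ in length, since Section 5.5 opens PMP integration to all clinics at six months.

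**Conclusion.** The plan gives no assurance that the model-based standard error for the current-user interaction is valid. The missing patient level is plain from the text; the direction of the resulting error is not. Under the per-PCP assumptions, the ratio of true to model standard error runs from about 0.9 to 1.3-1.4. Ratios of 1.05 to 1.31 would raise the 2.5% level to about 3.3-8.7%, and a ratio of 0.90 would lower it to about 1.3%. The 1.69 in the clinic-level simulation needs monthly visits, strong correlation and no patient seen in both periods, so it is an outer bound rather than an expectation.

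The case for a change does not depend on the direction, since a misstated standard error in a primary analysis is worth correcting either way. It deserves a change to the specification but does not undermine the design.

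**What to change.** In the current-user models, base inference for the interaction on clinic-clustered robust standard errors with a small-sample correction suited to about 40 to 50 clinics. This allows for any correlation among visits within a clinic, whichever way the error runs, and needs no assumption about how a patient's visits correlate.

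The alternative is a patient random effect. In a three-category model it is needed for each non-reference logit, and it should link a patient's visits across PCPs rather than be nested within PCP. The coefficients then become conditional on the patient, and a constant intercept does not capture correlation that decays.

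Report visits per patient in each period and the share of patients seen in both, so that readers can judge how much the choice matters.

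The cost is a little more analysis work and intervals that may become somewhat wider. No new data are needed.
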